## 5 TRIAL DESIGN

This will be a phase 1a randomized, open label, multi-center study with approximately 24 subjects. All subjects will receive standard of care per institutional guidelines for treatment of patients with SARS-CoV-2 infection. In addition to standard of care, the brequinar group will receive brequinar 100 mg once daily for 5 days.

The Massachusetts General Hospital (MGH) COVID-19 Treatment Guidance is provided in [Appendix D Section 15.4](#). This guidance provides an example of standard of care instructions for treatment of COVID-19. The guidance is provided as informational only, it is not required that this guidance be used for treatment as standards of care may differ between institutions.

Subjects will have a Screening Visit followed as soon as possible with Study Day 1 (Day 1 may take place on the same day if entry criteria data are available). Study procedures are presented in detail in [Section 8](#). Subjects will be followed through Day 15, with mortality assessed via a phone call/other digital media acceptable to institution on Day 29.

If the subject is being discharged prior to Day 7, see [Section 8.5](#).

It is understood that some assessments may not be conducted if the subject is unable to return to the clinic after discharge due to restricted travel. If an assessment is missed due to after hospital discharge, e.g., samples or blood draws, this will not be counted as a protocol deviation. Any of the study visits may be conducted via telephone if the subject has been discharged from the hospital and is not permitted to or is unable to return to the hospital/clinic for these visits.

Information is to be collected using the electronic health record (EHR) whenever possible. It is not required to perform study-specific laboratory assessments, NEWS 2 assessments, etc. separately for study purposes.

PROTOCOL NUMBER: CCB-CRISIS-01  
PROTOCOL VERSION FINAL DATE: 10SEPT2020

Page 25 of 58

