## 8 STUDY TREATMENTS

### 8.1 Description of Study Medications

#### 8.1.1 Brequinar

Brequinar will be supplied as 100 mg capsules. Dosing will be a single 5-day course of brequinar 100 mg once daily for 5 doses. The initial brequinar dose (Day 1) should be administered as soon as possible based on study drug availability from the investigational pharmacy. At least the first dose of study medication is to be taken in the hospital. Subjects in the brequinar group discharged before Day 5 will be dispensed brequinar to take at home daily until all 5 doses have been taken.

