#### 8.4.2 Study-Level Stopping Criteria

Following assessment by the Data Safety Monitoring Board (DSMB, see [Section 10.9](#)), the study is to be stopped as shown below:

- If  $\geq 4$  subjects on the brequinar treatment arm develop the same Grade 3 or 4 adverse event or symptomatic laboratory abnormality
- If  $\geq 8$  subjects on the brequinar treatment arm develop any Grade 3 or 4 adverse event or symptomatic laboratory abnormality.

### 8.5 Hospital Discharge Prior to Study Day 15

Subjects discharged from the hospital prior to the Day 15 visit are to return to a research facility when feasible for the remaining study visits. All scheduled study assessments are to be completed at these visits when conducted at a research facility.

PROTOCOL NUMBER: CCB-CRISIS-01  
PROTOCOL VERSION FINAL DATE: 10SEPT2020

Page 30 of 58

For subjects in the brequinar treatment group discharged from the hospital prior to Day 5, the subject is to take home the remaining doses of brequinar for daily self-administration. All subjects (brequinar and SOC) should have the scheduled assessments, e.g. lab samples and the nasopharyngeal swab, on the day of discharge and enter these results on the appropriate EDC page. Following discharge, subjects are to return to the research or out-patient lab collection facility for the remaining study visits, if feasible. Out-patient lab results are to be entered into the EDC and reviewed by a member of the study team. It is important that every effort be made to have subjects return at least on Days 7 and 15, if feasible. Subjects in the brequinar group are to record brequinar dosing on the medication diary provided by the study team. The study team will arrange for the subject to return any unused study medication to the research facility.

For all subjects, if discharge occurs on Days 10, 11, or 12, ensure a hematology/chemistry sample has been obtained on the day of discharge and record these results on the appropriate EDC page. Following discharge, the subject is to return to the research or out-patient lab collection facility for the Day 15 visit, if feasible. Out-patient lab results are to be entered into the EDC and reviewed by a member of the study team.

If discharge occurs on Days 13, 14 or 15, complete the Day 15 Final Visit activities prior to discharge. No further visits are required unless follow up is needed for a study drug-related AE or an SAE; the Day 29 mortality assessment is still to take place.

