Subjects who are discharged from the hospital before Day 7 will have follow up contacts with study staff (phone calls or other digital media) on Days 7, 15 and 29. Early discharge subjects in the brequinar treatment group will also have samples for safety labs (hematology and chemistry) obtained either at the research facility or at an outpatient laboratory on Study Days  $7 \pm 2$  and  $15 \pm 2$ . The safety laboratory results are to be initially assessed in real time by the Principal Investigator or designated person and the Medical Monitor. Any study drug-related clinically significant out-of-range laboratories or study drug-related adverse events will be followed as needed until resolution or stable.

The in-hospital assessments and phone call visits will specifically ask about possible hematologic toxicity including any evidence of the list below. Early discharge subjects will be provided with a list of the following events in lay terms and will be instructed to call the research team if any of these events occur.

PROTOCOL NUMBER: CCB-CRISIS-01  
PROTOCOL VERSION FINAL DATE: 10SEPT2020

Page 45 of 58

- Ecchymosis/purpura/petechiae
- Epistaxis
- Hemoptysis
- Hematuria
- Gingival bleeding
- Prolonged bleeding time from needle sticks, abrasions or lacerations
- Hematemesis
- Rectal bleeding
- Blood in stool
- Any other unusual bleeding noted by the subject or caregiver

Any of these symptoms considered clinically significant will be recorded as an adverse event and must be followed until resolved or stable.

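### Section 10.8 gives the take-home bleeding list and the instruction to call only to early-discharge subjects, which reads as discharge before Day 7, while Section 8.5 handles any discharge before Day 15

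*Protocol*

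**What the plan says.** Section 10.8 of the current version (10 September 2020) sets out follow-up for haematologic toxicity in this order:

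- **Contacts.** "Subjects who are discharged from the hospital before Day 7 will have follow up contacts with study staff" on Days 7, 15 and 29.
- **Laboratory samples.** "Early discharge subjects in the brequinar treatment group will also have samples for safety labs (hematology and chemistry") around Days 7 and 15.
- **Questioning.** "The in-hospital assessments and phone call visits will specifically ask about possible hematologic toxicity including any evidence of the list below". This applies to everyone.
- **Take-home list.** "Early discharge subjects will be provided with a list of the following events in lay terms". The same sentence has them told to phone the study team should a listed event happen. The list is of bleeding signs.

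Section 8.5 uses a different range: "Subjects discharged from the hospital prior to the Day 15 visit are to return to a research facility when feasible" for the visits that remain. It has separate provisions for discharge on Days 10 to 12 (a blood sample on the day of discharge, then a Day 15 visit if feasible) and on Days 13 to 15 (Day 15 activities done before leaving, with no routine visit afterwards). It mentions neither the list nor an instruction to call.

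Section 5 keeps the narrower cut-off in its pointer to Section 8.5: "If the subject is being discharged prior to Day 7, see" that section. The closing line of the visit schedule in Section 9.5 points to the same section for any discharge before Day 15.

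**The concern.** Rates of post-randomisation adverse events are part of the primary endpoint (Section 6.1). After discharge, an event is captured only if someone asks or the subject reports it. Section 3.7 names thrombocytopenia, with mucositis, as the main dose-limiting toxicity in earlier weekly-schedule studies, and Section 8.2.1 reports two deaths attributed to haemorrhage in a once-weekly study. Bleeding is what the list in Section 10.8 exists to catch.

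If the list goes only to those discharged before Day 7, prompted self-report depends on the day of discharge, and the protocol gives no reason why it should. The protocol still treats the later period as relevant: it schedules Day 15 safety laboratory tests and collects all adverse events through Day 15, then serious or drug-related ones. What is at stake is delayed or lost reporting of bleeding between discharge and the next contact.

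**Working it through.** The protocol gives no figure to reproduce. The check is a comparison of passages and a count of days.

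**Step 1: who is an early-discharge subject?** Section 10.8 has no definition. Its only discharge cut-off is before Day 7, in the sentence on contacts. The next sentence uses the term for the first time, says these subjects will *also* have samples, and places the first sample at Day 7 ± 2. An outpatient sample at about Day 7 fits a group that left before then. The list-and-call sentence, one paragraph later, uses the same term. The inference that it means discharge before Day 7 is strong, but it remains an inference.

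**Step 2: does another section extend the list?** Section 8.5 does not. Nor do Section 3.9, Section 9.5 or the Schedule of Events (Appendix A).

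**Step 3: is dosing over by then?** Section 8.1.1 states: "Dosing will be a single 5-day course of brequinar 100 mg once daily for 5 doses". A brequinar subject discharged on Day 7 or later has normally finished the planned course. This step concerns the brequinar arm only.

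**Step 4: how long until the next scheduled bleeding question?**

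| Day of discharge | Next scheduled contact | Interval |
|---|---|---|
| 7 | Day 15 | 15 − 7 = 8 days |
| 12 | Day 15 | 15 − 12 = 3 days |
| 13 | Day 29 survival check | 29 − 13 = 16 days |
| 14 | Day 29 survival check | 29 − 14 = 15 days |

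The Day 15 window is ± 2 days, so the Day 7 interval can reach 17 − 7 = 10 days. For Days 7 to 12 the Day 15 return is conditional on feasibility, with phone contact as the fallback. Missed post-discharge assessments are not counted as deviations (Sections 5 and 9.6). For Days 13 and 14 no Day 15 contact follows discharge. Section 9.5 asks only for survival status at Day 29 and allows it to be taken from the health record without a call.

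**Step 5: what is one subject worth?** With about 16 brequinar and 8 standard-of-care subjects, one subject is 1/16 = 6.25 percentage points or 1/8 = 12.5 percentage points of an arm. That is the weight of a single subject, not an estimate of how many events would be missed.

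**The case against.** The strongest reply is that the term is undefined and may have been meant to cover any discharge before Day 15, the class that Section 8.5 and the end of Section 9.5 treat as needing special handling. That is possible, and it would be wrong to say that Section 10.8 *defines* early discharge as before Day 7. But a site reading Section 10.8 in order would apply Day 7, and on either reading the two sections need reconciling.

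A second reply is that the gap is partly covered, and this stands:

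- Everyone is asked about bleeding in hospital and at phone visits.
- Haematology is collected daily through Day 7 unless the clinician stops it, so a subject still in hospital then will usually have counts from after dosing.
- Section 3.9 requires a discharge-day sample from brequinar subjects who leave before completing the study, and allows extra visits for haematologic toxicity.
- Section 9.5.1 permits unscheduled visits for drug-related or serious events with onset within two weeks of the last dose.

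Unscheduled and extra visits, however, help only once an event is known, and the list and the call are the means by which the subject makes it known.

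Third, experience at or below this daily dose over five days was one mild thrombocytopenia in 39 subjects (Section 3.6.2), so few bleeding events may be expected. That limits the likely yield but does not explain a cut-off at Day 7.

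A reader might also infer a bias between arms. The text does not support that: the list-and-call sentence has no arm restriction. Nor can one conclude that later-discharge subjects receive no instruction from any source, because the subject information sheet and consent form are not shown.

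**Conclusion.** The point holds as a gap between Sections 10.8 and 8.5. Read as written, subjects discharged on Days 7 to 12 leave without the list or the instruction to call and wait 3 to 8 days for the next scheduled bleeding question. Those discharged on Days 13 and 14 have no prompted question required after discharge. This rests on reading early discharge as before Day 7, which the context supports strongly but does not state, and on the protocol text alone.

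Two stronger readings do not hold. One is that bleeding after any Day 7 to 14 discharge is known only by recall at Day 15: for Days 13 and 14 there is no later Day 15 contact, and for the others laboratory samples and earlier questioning also contribute. The other is that the adverse event rate would be wrong by 6.25 or 12.5 percentage points: the number of subjects discharged in this range, and the number of events a leaflet would recover, are unknown. This is an inexpensive improvement to safety-event capture, not an error in the statistical plan.

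**What to change.** In Section 10.8, replace the subject of the list-and-call sentence so that it covers all subjects discharged before or at the Day 15 visit. The sentence already applies to both arms, so no wording about arms is needed. Where the term early discharge remains in that section, state the day it refers to, and add to Section 8.5 a short cross-reference to the list so that the two sections agree.

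The essential change is one phrase. Its running cost is a leaflet, already planned, handed to more subjects at discharge. No dose, visit, laboratory schedule or stopping rule changes.

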## 2 SYNOPSIS

CCB-CRISIS-01 SYNOPSIS	
IND	149291
Title	The CRISIS Study: A randomized open-label study assessing the safety and anti-coronavirus response of suppression of host nucleotide synthesis in hospitalized adults with coronavirus-19 (COVID-19)
Protocol	CCB-CRISIS-01
Rationale	
Brequinar is a potent DHODH inhibitor that has been studied in more than 1,000 cancer, psoriasis, and organ transplant patients. DHODH inhibition has been extensively studied as a potential therapeutic target in the treatment of RNA-based viruses. The inhibition of DHODH is effective in inhibiting viral replication in pre-clinical models involving many RNA-based viruses with nanomolar potency and a high selectivity index. In these pre-clinical models, the benefit of DHODH inhibition can be reversed by the supplementation of exogenous nucleotides, confirming that the on-target effect of host pyrimidine depletion is key to the anti-viral activity. The primary dose-limiting adverse effects have included thrombocytopenia and mucositis.
 
The CRISIS trial will study standard of care (SOC) and SOC with 5 days of DHODH inhibition. Clear Creek Bio hypothesizes that a defined 5-day course of brequinar will inhibit the enzyme DHODH to a degree sufficient to result in the transient depletion of host pyrimidine nucleotides, thereby inhibiting viral replication. A recent publication demonstrated that inhibitors of DHODH could potentiate the activity of inhibitors of RNA-dependent RNA polymerase (RdRp) in the treatment of dengue virus, another single-stranded RNA virus similar to SARS-CoV-2. This inhibition of viral replication may restore the balance in favor of the host immune system for the clearance of SARS-CoV-2.
 
Marketed DHODHi medications are available, including leflunomide or teriflunomide, however these are very weak inhibitors of DHODH with cellular potency ~500 times lower than brequinar. These low potency inhibitors of DHODH are not expected to have the ability to acutely lower the pool of intracellular pyrimidines to the degree that is required for decreasing the viral load associated with SARS-CoV-2 infection, making brequinar the better choice for acute SARS-CoV-2 infection. Brequinar has not been previously tested as an anti-viral.

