### 3.6.2 Risk/Benefit of Brequinar

As presented in the Brequinar IB [5], an extensive database exists with more than 800 cancer patients exposed to this compound for treatment of a variety of solid tumors at various treatment regimens, doses, and routes including a single dose, once weekly, twice weekly, single dose every 3 weeks, daily times 5 every 4 weeks, and daily times 21 days for multiple courses. Brequinar has also been utilized at lower doses than used in the cancer studies in psoriasis and organ transplant. The maximum intravenous dose given was 2,250 mg/m^2 every 3 weeks, and the maximum oral dose was 100 mg/m^2 daily for 21 days. While no DHODHi has been tested to date in the clinic for infection with SARS-CoV-2 and no brequinar safety information is available in treatment of this disease, DHODHi therapy in the context of trials for patients with cancer has the expected safety side-effects of mucositis and bone marrow suppression. However, the prior clinical experience in 39 subjects who received daily brequinar for 5 consecutive days at or lower than 100 mg/day show no mucositis and only 1 (2.6%) episode of mild thrombocytopenia. The 100 mg per day dose proposed for administration in this study should be safe and well tolerated.

The possible benefit in using brequinar to treat SARS-CoV-2 infection is the hypothesis that a 5-day period of brequinar dosing will suppress host *de novo* pyrimidine synthesis for this period thus decreasing viral load. As discussed above, inhibition of DHODH is expected to reduce the ability of the virus to replicate and it is for this reason that study CCB-CRISIS-01 will administer brequinar to patients with COVID-19.

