### 3.7 Risks Associated with Participation in the Clinical Study

In studies utilizing the weekly schedule of administration of brequinar in patients with refractory solid tumors, reversible myelosuppression, in particular thrombocytopenia, and mucositis have

PROTOCOL NUMBER: CCB-CRISIS-01  
PROTOCOL VERSION FINAL DATE: 10SEPT2020

Page 21 of 58

been the primary dose-limiting toxicities. In addition, skin rash, nausea/vomiting, fatigue, and leukopenia have been dose-limiting in trials utilizing other schedules of brequinar administration. However, these effects were self-limiting, transient, required treatment in few cases, and resolved following discontinuation of dosing. These adverse effects have been associated with higher doses of brequinar given via the intravenous route and for longer durations than the 100 mg dose and 5-day regimen proposed for this study.

COVID-19 patients are at higher risk of complications and poor outcomes when their infection is combined with comorbidities including hypertension, diabetes, chronic kidney disease, chronic obstructive pulmonary disease (COPD) or asthma, cardiovascular disease (coronary artery disease or congestive heart failure), liver cirrhosis, age > 65, and BMI > 30 [15]. It is likely that participants in this protocol who are sick enough to be hospitalized will have at least one of these comorbidities.

A comprehensive safety monitoring plan will be utilized in this study to assess the ongoing safety and well-being of participants (see [Section 10.8](#)).

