### **10.8 Safety Monitoring for Hematologic Toxicities**

Myelosuppression is a known effect of DHODH inhibition that is associated with prolonged exposure and high doses. To reduce the risk of this effect with brequinar in COVID-19 subjects, the extensive brequinar safety database with over 1,000 patients has been evaluated to select a dose level expected to be safe and well tolerated with regard to hematologic toxicity. In addition to enhancing safety by selecting a relatively brief 5-day exposure and a low brequinar dose, all subjects in the clinical trial will initially be hospitalized as in-patients and will be under the care of highly qualified infectious disease, critical care, and associated medical personnel. As is standard of care for moderately to severely ill in-patients, daily samples will be obtained for hematology assessments including complete blood count with full differential (WBC, RBC, hemoglobin, hematocrit, platelet count, absolute neutrophils, absolute lymphocytes, absolute monocytes, absolute eosinophils, and absolute basophils). Any clinically significant out-of-range laboratory values will be assessed by hospital staff in a timely manner and treatment needs addressed as appropriate. Clinically significant out-of-range laboratory results will be reported as adverse events.

In addition to real time assessments by the treating clinical team, the Clear Creek Medical Monitor will assess the available hematology data on a weekly basis to identify any pathologic trends or safety issues. Any apparent increase in the expected rate or severity of hematologic safety events will be discussed with the Principal Investigators, the Sponsor, and the Medical Monitor. In addition, the Data Safety Monitoring Board will assess available hematology data on a periodic basis to independently assess any pathologic trends or safety issues. If the rate or severity of hematologic toxicities appears to be above the expected rate or the severity appears worse than that expected, the trial enrollment will be suspended and no further subjects will be treated while a comprehensive data review is conducted. Depending on the outcome of the safety review the study may be stopped, the design adjusted, or the study may continue as designed. Individual and study stopping rules are provided in [Section 8.4](#).

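### The call-in list given to early-discharge subjects (Protocol 10.8) covers bleeding only and prompts no call for fever or new infection, nor, secondarily, for mouth sores

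*Protocol*

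**What the plan says.** All references are to the protocol version dated 10 September 2020.

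- **Subject of the section.** Section 10.8 opens with the statement "Myelosuppression is a known effect of DHODH inhibition".
- **Questions put by staff.** In-hospital assessments and phone visits "will specifically ask about possible hematologic toxicity including any evidence of the list below".
- **Handout.** "Early discharge subjects will be provided with a list of the following events in lay terms", and these subjects "will be instructed to call the research team if any of these events occur". The text does not restrict the handout to one arm.
- **Content.** There are ten bullets, the last being "Any other unusual bleeding noted by the subject or caregiver".
- **Dosing at home.** Section 8.1.1 requires only the first dose to be taken in hospital. Sections 8.1.1 and 8.5 have brequinar subjects discharged before Day 5 take the remaining doses at home.
- **Risk profile.** The Synopsis says "The primary dose-limiting adverse effects have included thrombocytopenia and mucositis", and Section 3.7 repeats the pairing. Section 8.2.1 includes leukopenia, granulocytopenia, stomatitis and infection among the adverse events commonly seen with the drug.
- **Reassurance at this dose.** Section 3.6.2 reports that "39 subjects who received daily brequinar for 5 consecutive days at or lower than 100 mg/day show no mucositis". Section 3.7 describes the dose-limiting effects as "associated with higher doses of brequinar given via the intravenous route and for longer durations" than planned here.

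**The concern.** Myelosuppression has more than one clinical face. Low platelets show as bleeding; low neutrophils show as fever or infection. The Section 10.8 list gives the discharged subject the first and leaves out the second, so it covers only part of the section's own subject.

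The omission of mouth sores is a secondary matter. Mucositis is not a hematologic toxicity, so a section with this title need not cover it. But no other list in the pages shown tells a discharged subject which symptoms to call about, and the protocol names mucositis beside thrombocytopenia as a leading toxicity.

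What is at stake is the timing and completeness of symptom reports between scheduled contacts through Day 15, the period over which all adverse events are collected for the primary safety endpoint. Daily adverse event review under Section 9.5 runs only until discharge. After that, between contacts, a report depends on the subject deciding to call, and the handout is the protocol's stated prompt for doing so.

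**Working it through.** The plan states no figure to reproduce here. The check is a count, a comparison of sections, and one side calculation.

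**1. Classify the ten entries in Section 10.8.**

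| Entry | Bleeding sign | Fever or infection | Mouth sores |
|---|---|---|---|
| Ecchymosis, purpura, petechiae | yes | no | no |
| Epistaxis | yes | no | no |
| Hemoptysis | yes | no | no |
| Hematuria | yes | no | no |
| Gingival bleeding | yes | no | no |
| Prolonged bleeding after needle sticks or cuts | yes | no | no |
| Hematemesis | yes | no | no |
| Rectal bleeding | yes | no | no |
| Blood in stool | yes | no | no |
| Other unusual bleeding (catch-all) | yes | no | no |
| **Total** | **10 of 10** | **0 of 10** | **0 of 10** |

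Gingival bleeding concerns the mouth, but it is a bleeding sign and would not lead a subject to report ulcers. The catch-all cannot rescue the other two columns, because it too is confined to bleeding.

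**2. Compare with the toxicities the protocol names.** Thrombocytopenia (Synopsis, 3.7, 8.2.1) is matched by all ten entries. Granulocytopenia, leukopenia and infection (8.2.1) are matched by none. Mucositis or stomatitis (Synopsis, 3.7, 8.2.1) is matched by none.

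**3. Doses that can fall outside the hospital.** Five doses are planned and at least one is given in hospital: 5 − 1 = 4, so up to 4 of 5 (80%). This is the extreme case, not an expected share. As context, the 06 July 2020 version carried the same ten entries while its Section 9.5 forbade giving drug to take home. Home dosing came in with the 31 July 2020 version and the list did not change.

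**4. What the prior data say about mucositis.** Section 3.6.2 gives 0 of 39 at or below 100 mg/day for 5 days. The exact two-sided 95% upper limit is 1 − 0.025^(1/39) = 0.0903, or 9.0%. So zero observed does not mean zero risk, but the limit transfers poorly. The 39 appear to be the subjects from the three intravenous studies in Section 8.2.1 (same count, same single thrombocytopenia), and the figure covers mucositis of any grade. For the oral route used here, Section 8.2.1 reports stomatitis in one subject at this dose level, with no denominator, grade or dosing duration. No event rate for this trial follows from either source.

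**The case against.** **The list does what its section title promises.** The title and lead-in confine it to hematologic toxicity. This stands for mouth sores, which is why they are secondary here. It does not stand for fever and infection, because the section itself opens with myelosuppression.

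**Other safeguards cover the same ground.** Section 10 has subjects questioned about adverse events generally, and Section 10.2 has new infections captured. The staff questions are worded to include the list, not to be confined to it. Section 8.5 moves visit activities to phone when a subject cannot return, and Appendix 15.1 schedules assessments on Days 3, 5 and 7 and allows any visit after Day 1 by phone. Early-discharge brequinar subjects have safety laboratory tests on Days 7 ± 2 and 15 ± 2, and hematology includes a full differential (9.4). All of this stands and narrows the gap, but these safeguards act at contacts, whereas the handout acts between them. A reader might infer that a discharged subject has no contact before Day 7. The documents do not support that: Sections 9.6 and 10.8 name only the later days, but Section 8.5 and Appendix 15.1 together make contacts on Days 3 and 5 likely, though not clearly stated.

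**Consent materials may say more.** The consent form and information sheet are not shown. This stands; the point is limited to the Section 10.8 list.

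**Risk at this dose is low.** This also stands and keeps the point small.

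**Prompted calls would mostly report COVID-19.** Fever and sore throat are among the entry symptoms in Section 7.2. This is a real cost, taken up under the fix.

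**Conclusion.** The point holds as a minor but specific safety improvement. Ten of ten call-in entries are bleeding signs and none prompts a call for fever or new infection, although the section's own subject and the listed common adverse events call for one. The omission of mouth sores is a weaker, secondary part of the same point.

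Three stronger readings are tempting and are not supported.

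- A reader might infer that the omission disables the individual stopping rule in Section 8.4.1 during home dosing. That would need symptomatic Grade 3 or 4 toxicity to appear while home doses remain, and the protocol gives no onset timing.
- A reader might take 9.0% as a plausible mucositis rate for this trial. It is an any-grade upper limit from what appear to be intravenous subjects.
- A reader might infer bias between the arms. The handout goes to early-discharge subjects without distinction of arm.

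The conclusion assumes that the Section 10.8 list is the only symptom call-in instruction, which is true of the pages shown. Wider advice in the consent materials would shrink the point further.

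**What to change.** In both arms, add two entries to the Section 10.8 question list and to the handout:

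- *new or worsening fever, chills or other signs of new infection*;
- *new or worsening mouth sores or pain on swallowing*.

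Widen the lead-in to match, so that staff ask about possible hematologic toxicity, mucositis or infection. If only one entry is accepted, it should be the first, which lies within the section's existing scope.

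The change is two lines in an existing script and handout, with no new visit, sample or analysis. The downside is more low-grade events recorded that overlap with COVID-19 symptoms. The words *new or worsening* limit this, though they leave the judgment to a subject at home. Asking the same questions in the standard-of-care arm gives a reference, a thin one with about 8 subjects.
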